4.1.3.2 Presentation of Results

1) Summary statistics on NCOD and (non-normalized) cumulative OCS dose (COD) will be provided.

An ANCOVA model with factors for treatment and the stratification variables will be applied on NCOD. Least square (LS) means and standard error (SE) with 95% 2-sided CI for placebo and efgartigimod will be reported, along with the difference in LS means of IMP vs placebo (with SE), 95% 2-sided CI, and 2-sided p-value.

The supplementary analysis (using the treatment policy strategy) will be analysed in a similar way (descriptive statistics and ANCOVA). This supplementary estimator is not considered in the family wise alpha control.

2) Frequency tabulations will be provided for the percentages of participants within each outcome of IGA-BP per analysis visit. Additionally cumulative percentages (starting with the best outcome result) will be calculated. For participants who received rescue therapy, only assessments prior to or on the start date of rescue therapy will be considered.

Frequency tabulations will be provided of the percentage of participants that have achieved IGA-BP score of 0 while receiving efgartigimod PH20 SC or placebo and have been off OCS therapy for ≥8 weeks at week 36.

The same stratified CMH as for the primary endpoint will be performed.

All IGA-BP data will be listed.

[figure not shown]
3) Frequency tabulations will be provided of the percentage of participants that have achieved control of disease activity (CDA) while receiving efgartigimod PH20 SC or placebo and remain free of relapse through week 36.

The same stratified CMH as for the primary endpoint will be performed.

4) Frequency tabulations will be provided of the percentage of participants that have achieved CR while receiving efgartigimod PH20 SC or placebo and while receiving minimal OCS therapy for ≥8 weeks (CRmin) at week 36.

The same stratified CMH as for the primary endpoint will be performed.

5) Descriptive statistics will present the actual values and changes from baseline of the itch NRS 24-hour average score per analysis visit. For participants who received

rescue therapy, only assessments prior to or on the start date of rescue therapy will be considered.

Changes from baseline in the 24-hour average itch NRS score will be analysed using a mixed-effect model for repeated measurements (MMRM). The least square means on changes from baseline at week 36 will be calculated as well at the other analysis visits (with no strict control of alpha of these). The MMRM model will include treatment by visit and baseline value by visit interaction terms, and the two stratification factors as covariates. Within-subject correlation will be modeled using the R matrix. With 13 post-baseline visits during the treatment-phase, a standard unstructured covariance matrix would require 91 variance parameters. Therefore, a modified unstructured covariance matrix (UN) will be used: ANTE(1).

Least square means, SE, and 95% 2-sided CI for placebo and efgartigimod will be reported by analysis visit, along with LS means of the between-arm difference including also with SE, 95% 2-sided CI, and 2-sided p-value. If the default Newton-Raphson algorithm used by SAS PROC MIXED fails to converge, the following will be tried to avoid lack of convergence while maintaining an unstructured variance:

The Fisher scoring algorithm (via the SCORING = 5 option of the PROC MIXED statement) will be used to obtain the initial values of covariance parameters. In the rare case where the above fails, the following covariance structures will be tested for convergence (in order): toeph, arh(1), csh, toep, ar(1) and cs).

[figure not shown]
All itch NRS data will be listed.

Subgroup tables will be created for all key secondary endpoints (not for supplementary analysis).

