6.8.1.3. Oral Prednisone Dose Adjustment Regimen (Based on BP Disease Assessment)

Participants will receive IMP with concurrent OCS therapy. The recommended OCS dosing regimen is described below and displayed in Table 7.

The investigator should not deviate from the concurrent oral prednisone dosing regimen, except in matters where the safety of the participant may be compromised. After taking appropriate action to ensure the safety of the participants, such concerns should be documented and communicated to the sponsor's medical monitor and designee within 24 hours of the event.

For OCS doses not listed in Table 7, minimum and maximum recommended doses are provided. For participants with body weights of <45 kg or ≥110 kg, the investigator should propose OCS doses and inform the medical monitor to ensure consistency within the study.

Note: For the following list, "oral prednisone" refers to prednisone or an alternate OCS of equivalent dose strength.

- All participants will begin the study by taking oral prednisone 0.5 mg/kg/day starting at baseline (week 0; day 1).
- If the participant has not achieved CDA within 1-3 weeks of treatment with oral prednisone 0.5 mg/kg/day, then the dosage may be increased to 0.75 mg/kg/day for up to an additional 3 weeks. This period may be extended by 1 additional week (based on clinical judgment) to achieve CDA with an oral prednisone dosage of either 0.75 mg/kg/day or 1 mg/kg/day.

- A participant will be considered as a treatment failure if they do not achieve CDA after receiving the IMP with the prednisone dosing regimen described above. In case of treatment failure, IMP will be permanently discontinued (Section 7.1.1). Under these circumstances, the participant will be considered a nonresponder (Section 9.3.2).
- When CDA is achieved, the oral prednisone dosing regimen is adjusted as follows:
 - After CDA has been sustained for ≥2 weeks, the dose tapering schedule begins with the next lower oral prednisone dosage as listed in Table 7. Each new dosage must be maintained for at least 2 weeks provided that no new lesions (transient or nontransient) appear. Duration of tapering steps from escalated doses (>0.5 mg/kg/day) may be shortened based on clinical judgment.

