9.3.3. Secondary Endpoints Analysis

9.3.3.1. Analysis of Secondary Efficacy Endpoints (Part B Only)

For part B, there are 5 proposed key secondary endpoints subject to alpha control:

- 1. Cumulative dose of OCS from baseline to week 36.
- 2. Proportion of participants who achieve an IGA-BP score of 0 while receiving efgartigimod PH20 SC or placebo and have been off OCS therapy for ≥8 weeks at week 36.
- 3. Proportion of participants who achieve CDA while receiving efgartigimed PH20 SC or placebo and remain free of relapse through week 36.
- 4. Proportion of participants who are in CR while receiving efgartigimed PH20 SC or placebo and have been receiving minimal OCS therapy for ≥8 weeks at week 36.
- 5. Changes from baseline in the 24-hour average itch score from the Itch NRS.

Details on how to deal with the main ICEs for the proposed key secondary endpoints will be provided in the SAP.

The first proposed key secondary endpoint—cumulative dose of OCS from baseline to week 36— will be analyzed in the form of a normalized cumulative OCS dose (NCOD), normalizing by weight and by number of days in study and will be denoted as NCOD.

For the NCOD endpoint, the analysis of covariance (ANCOVA) model will be used to compare both study arms. The model will include treatment and the stratification variables will be considered as factors. Other secondary efficacy endpoints will be analyzed in a similar fashion, as described below:

- Cumulative OCS dose at the time the participant exhibits CDA, CR, and CR while receiving efgartigimod PH20 SC or placebo and receiving minimal OCS therapy for >8 weeks
- CR/PR while receiving efgartigimod PH20 SC or placebo and off OCS therapy for >8 weeks
- Relapse

In addition to using the measure NCOD for analyzing the cumulative dose of OCS use over the study duration, the term "cumulative OCS use (mg)" will be used and analyzed using descriptive statistics.

The second, third, and fourth proposed key secondary endpoints will be analyzed using a CMH test as specified for the primary endpoint. Other secondary efficacy endpoints that are expressed as responder proportions will be analyzed similarly.

The fifth proposed key secondary endpoint—changes from baseline in the 24-hour average itch score from the Itch NRS—is measured over time and will be analyzed using a mixed-effect model for repeated measures, and the least squares mean difference will be estimated at the prespecified time point.

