3.2 DEMOGRAPHIC AND OTHER BASELINE CHARACTERISTICS

3.2.1 Available data

The following parameters will be available:

- Demographics: sex at birth, age at informed consent, race and ethnicity (if collection permitted), childbearing potential, date of last menses (listed only), height, weight and BMI at screening, year of birth (listed only), date of signing ICF (listed only).
- Baseline disease characteristics: date of BP disease onset and diagnosis (listed only), BP disease history (newly diagnosed / relapsing), number of relapses in participant's history, Karnofsky performance status score, BPDAI activity and total score at baseline, BP disease severity at screening (moderate / severe; as determined by IGA-BP=3/4 and collected on the Disease History form), IGA-BP at baseline (collected on IGA-BP form), itch NRS 24-hour average and worst score at baseline, OCS dose at baseline (mg), OCS dose per body weight at baseline (mg/kg), anti-BP180 antibodies at baseline, anti-BP230 antibodies at baseline.

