4. EFFICACY, PHARMACOKINETIC, PHARMACODYNAMIC AND IMMUNOGENICITY ANALYSES

4.1 EFFICACY AND QUALITY OF LIFE

All efficacy endpoints will be analyzed on the FAS population. The primary endpoint and all 5 key secondary endpoints will also be analyzed on the PP population as sensitivity analysis.

Wherever the stratification factors will be used in the efficacy analyses, the actual values of these will be used and not the ones coming from the randomization. Also, for participants randomized without stratification, i.e., part A participants and Japanese or Chinese Part B participants, these factors will be derived in order to include these participants in the statistical models.

For all references to weeks, analysis visits are considered as described in section 2.2.4, unless specified otherwise. If multiple assessments fall within the same analysis window, only the assessment closest to the target date will be considered unless specified otherwise. Other assessments within this window will only be listed and not considered in the below analyses. Only the time to response endpoint (see section 4.1.4) will be derived using all possible measurements and not only the one closest to the target of the analysis visit. Only visits up to Week 36 analysis visit will be considered defining the different responses. For endpoints 'at week 36', the last non-missing analysis visit assessment from week 32 till week 36 will be used.

All endpoints/estimands defined as an event 'while receiving efgartigimod PH20 SC or placebo' should be handled as follows: treatment discontinuations not due to 'lack of efficacy' (but e.g., due to AE) are still considered as 'while receiving efgartigimod PH20 SC or placebo'.

[figure not shown]
Examples of SAS code for the statistical analysis procedures are provided in appendix 9.3.

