4.1.2.3 PRESENTATION OF RESULTS

The primary endpoint will be analyzed on the FAS population and additionally on the PP population as sensitivity analysis.

A frequency tabulation will be provided for the disease status as collected in the CRF per analysis visit. This includes the status 'CR while being off OCS therapy for at least 8 weeks'. For participants who received rescue therapy, only assessments prior to or on the start date of rescue therapy will be considered.

Frequency tabulations will be provided of the percentage of participants who are in CR while receiving efgartigimod PH20 SC or placebo and have been off OCS therapy for ≥8 weeks at week 36 (composite strategy - primary endpoint). The table will be repeated for subgroups, including treatment differences in proportions with 95% Wald CI (with continuity correction).

The proportion of participants with BP who are in CRoff at week 36 will be tested by means of a Cochran-Mantel-Haenszel (CMH) test stratified for the 2 stratification factors of disease history (newly diagnosed versus relapsing) and disease severity as per IGA-BP at screening (moderate versus severe). The common (conditional) odds ratio will be provided, along with the exact 95% CI and 2-sided p-value from the CMH association test. In addition, the Klingenberg 95% CI for the strata-adjusted difference of proportions along with its midpoint estimate will be provided. Homogeneity of the odds ratios will be tested by means of a Breslow-Day test with Tarone's adjustment.

A sensitivity analysis will be performed on this primary endpoint using exact logistic regression with fixed effect terms for randomized treatment and stratified for the 2 stratification factors of disease history and disease severity as per IGA-BP at screening. Treatment groups will be compared in terms of the (conditional) odds ratio with 95% CI. A non-linear model with fixed effect terms for randomized treatment and the 2 stratification factors will be fitted to obtain the estimated treatment difference in proportions with 95% CI.

The same CMH test as for the primary analysis will be applied for the supplementary analysis (using a treatment policy strategy).

All sensitivity and supplementary analyses for the primary endpoint will be performed both for the analysis of study Part A, study Part B and pooled study Part A and B.

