4.1.6 Subgroup analyses for efficacy

Subgroups are defined based on the following categorizing factors:

- Disease history (newly diagnosed versus relapsing)
- Disease severity as per IGA-BP at screening (moderate versus severe)
- BPDAI activity score at baseline: <20, 20-56, >56
- Geographical region (Asia, North America, EU region+UK, Rest of world)
- Sex at birth
- Age at informed consent (18 <65, 65 <75, 75 <85, >=85)
- BMI at screening (Underweight: < 18.5 kg/m², Normal weight: 18.5 -< 25 kg/m², Overweight: 25 -< 30 kg/m² Obese: >= 30 kg/m²)
- Race (Asian, Black or African American, White, Other)

Subgroup analyses will be performed on the primary and key secondary efficacy endpoints.

SGS	Statistical Analysis Plan	
ARGX-113-2009	Final and Interim Analysis	Final 4.0 of 04NOV2024

Following table summarizes the analyses:

Table 4: Summary of (subgroup/supplementary) analyses

[figure not shown]
Subject level variable	Estimand	Estimator
CRoff at week 36	Composite	CMH ^{1,p,s} Logistic regression
	Treatment policy	MI + CMH
NCOD	While on treatment	ANCOVA ^{2,p,s}
	Treatment policy	ANCOVA
IGA-BP score of 0 at week 36 while off OCS therapy for ≥8 weeks	Composite	CMH ^{2,p,s}
CDA and remain free of relapse through week 36	Composite	CMH ^{2,p,s}
CRmin at week 36	Composite	CMH ^{2,p,s}
Itch NRS 24-hour average score	Treatment policy	MMRM ^{2,p,s}
IGA-BP score of 0 or 1 at week 36 while off OCS therapy for ≥8 weeks	Composite	CMH
IGA-BP score of 0 or 1 at any time through week 36	Composite	CMH
BPDAI activity and total score/Itch NRS worst score	Treatment policy	MMRM
Time to CDA/CR	Composite	Gehan-Wilcoxon
Time to relapse from CDA/CR/CRoff	Treatment policy	Log-rank
Other time to event	Composite	Log-rank
NCOD for subperiods	While on treatment	ANCOVA
Received rescue therapy before week 36	Treatment policy	CMH
QoL	Treatment policy	MMRM
C-GTI	Treatment policy	ANCOVA

¹ Primary endpoint

² Key secondary endpoint for study Part B

^p Also analysis on PP analysis set will be performed.

s Also subgroup analyses will be performed. No inferential statistics will be calculated for the subgroup analyses.

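### The NCOD ANCOVA adjusts only for two binary stratification factors; adding the baseline BPDAI activity score as a continuous covariate could gain some precision

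*SAP*

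**What the plan says.** SAP 4.1.3.2, item 1, gives the NCOD model: "An ANCOVA model with factors for treatment and the stratification variables will be applied on NCOD". Protocol 9.3.3.1 agrees: "The model will include treatment and the stratification variables will be considered as factors". SAP 4.1.2.3 names the factors as "disease history (newly diagnosed versus relapsing) and disease severity as per IGA-BP at screening (moderate versus severe"). SAP 4.1 adds: "Wherever the stratification factors will be used in the efficacy analyses, the actual values of these will be used". It also says the factors will be derived for participants randomized without them, so every participant can enter the model.

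Baseline disease activity is available on a finer scale. The schedule of activities has BPDAI at both screening and baseline. SAP 3.2.1 lists "BPDAI activity and total score at baseline" among the baseline characteristics, and SAP 4.1.6 uses it as a subgroup factor: "BPDAI activity score at baseline: <20, 20-56, >56". It does not appear in the NCOD model.

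The itch analysis, also a key secondary, does carry a continuous baseline term: "The MMRM model will include treatment by visit and baseline value by visit interaction terms, and the two stratification factors as covariates".

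**The concern.** NCOD depends on how the disease behaves. Under protocol 6.8.1.3 the dose may rise if control of disease activity (CDA) is not reached, tapering waits until CDA has been sustained, new lesions delay the taper, and relapse leads to an increase. A participant with more active disease at baseline could therefore be expected to accumulate more OCS. The starting dose cannot carry that information, because it is the same per kilogram for everyone: "All participants will begin the study by taking oral prednisone 0.5 mg/kg/day starting at baseline".

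The severity factor is a coarse and early measure of the same thing. Eligibility restricts IGA-BP to 3 or 4, so the factor has two levels, whereas the SAP provides for three bands of BPDAI activity. It is taken at screening, which can last up to 3 weeks, and OCS up to 0.3 mg/kg/day is allowed between screening and baseline (protocol 6.8.1). BPDAI also scores mucosal lesions, while the IGA-BP grades skin lesions (protocol 4.2.5).

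The stake is precision on an alpha-controlled endpoint. The documents state no SD, effect size or power for NCOD, so nothing shows that there is precision to spare.

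**Working it through.** **Is there a planned figure to reproduce?** Not for NCOD. Protocol 9.5 sizes Part B at 120 for the binary primary endpoint, and its response rates are blacked out. At the rates in the SAP 1.4.2.1 simulation (20% versus 50%), a Pearson chi-square test with 60 per arm has 94.1% power. That is consistent with the stated power above 90%, but it has no bearing on NCOD.

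**Inputs.**
- N = 120, 1:1, so 60 per arm (protocol 9.5, SAP 1.3); two-sided 5% (SAP 4.1.5).
- Planned model: intercept, treatment and two binary factors, so residual df = 120 - 4 = 116. With one more covariate, 115.
- r, the partial correlation of baseline BPDAI activity with NCOD given treatment and strata: not in the documents, assumed from 0 to 0.4.
- Power under the planned model: not in the documents, set to 80% or 90% for illustration.

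**Standard error.** The covariate multiplies the SE of the treatment difference by

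k = sqrt[(1 - r²) × (1 + 1/113)], with 113 = 115 - 2.

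The second term is the average price of estimating one more coefficient: sqrt(1 + 1/113) = 1.0044. At r = 0.3, k = sqrt(0.91) × 1.0044 = 0.9539 × 1.0044 = 0.958.

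**Power** (normal approximation). If the planned model has 80% power, the standardized effect is (1.960 + 0.842) × sqrt(2/60) = 0.511. With the covariate, power = Φ(2.802/k - 1.960). For 90%, replace 2.802 by 1.960 + 1.282 = 3.242.

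| r | Change in SE | Power if 80% as planned | Power if 90% as planned |
|---|---|---|---|
| 0 | +0.4% | 79.7% | 89.8% |
| 0.1 | -0.1% | 80.1% | 90.0% |
| 0.2 | -1.6% | 81.2% | 90.9% |
| 0.3 | -4.2% | 83.3% | 92.3% |
| 0.4 | -7.9% | 86.1% | 94.1% |

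**Break-even.** k = 1 when r² = 1 - 1/(1 + 1/113) = 1/114 = 0.0088, so r is about 0.09.

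**Overlap with IGA-BP.** Severity is already in the model, so r is smaller than the raw correlation between BPDAI and NCOD. A simulation assumed normally distributed BPDAI, an even severity split, and a correlation of 0.7 to 1.0 between BPDAI and the latent scale behind the IGA-BP split. A raw correlation of 0.3 left r at 0.19 to 0.25 (SE down 1.7% to 3.2% before the df cost). A raw correlation of 0.5 left 0.33 to 0.43 (5.5% to 9.7%). The r = 0.4 row therefore needs a raw correlation of roughly 0.5 or more.

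**The case against.** The strongest reply is that nothing is broken. Protocol and SAP agree on a valid model, type I error is controlled, and severity is already adjusted for. That stands. A reader who sees an ANCOVA with factors only might infer that it has no baseline adjustment at all. The documents do not support this: disease history and screening IGA-BP are both pre-treatment variables, so what is absent is a continuous covariate.

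The prognostic link is inferred. Dosing reacts to events after baseline, and CDA is defined by response (protocol 4.1.3), not by a threshold on baseline extent. No document reports a correlation between BPDAI and NCOD. This also stands, and it is why the gain is given only as a range that includes a small loss.

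The itch model is a weak precedent, since it adjusts for the baseline of its own outcome. NCOD has no informative baseline of its own, so using another instrument is a design choice. The comparison shows only that the SAP uses continuous baseline adjustment elsewhere.

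The change also reaches further than one line. SAP 4.1.4 applies the same ANCOVA to the C-GTI scores and the same analysis to NCOD in subperiods. SAP 1.4.3 ranks the key secondaries at the interim with the planned analyses. Both need a sentence in the SAP; neither is an obstacle.

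A worry about missing baseline BPDAI carries little weight. SAP 2.2.2 takes the last non-missing value before first dose, so a screening value already serves as the fallback.

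**Conclusion.** The point holds as a modest, optional improvement. The balance favours making the change: if BPDAI activity predicts nothing, the SE rises by about 0.4%. At r = 0.3 it falls by 4.2%, worth about 9% more participants (1/0.9582² = 1.089). The omission from the SAP and protocol text is certain. The size of the gain is not, because it rests on an assumed r, an assumed power under the planned model, and N = 120. The ANCOVA code in SAP 9.3.3 is not legible in the public copy, so the coded model could not be checked.

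Two stronger readings are tempting. A reader might infer that the plan is giving up a known amount of precision that could be had for nothing. The documents give no figure from which that amount could be known, and the covariate does cost a degree of freedom. A reader might also infer that, because NCOD is listed first, a miss on it blocks all the other key secondaries. SAP 1.4.3.2 and 4.1.5 set the Part B order by ascending interim p-value, so a miss blocks only the endpoints ranked after NCOD, and none if it is ranked last.

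**What to change.** Before Part B unblinding, amend SAP 4.1.3.2 (item 1), and the code in 9.3.3 to match, so that the NCOD ANCOVA has treatment, the two stratification factors and baseline BPDAI activity score as a continuous covariate. Apply this to both the while-on-treatment analysis and the treatment-policy supplementary analysis. Refer to SAP 2.2.2 for the definition of baseline; no further missing-value rule is needed while a screening value exists.

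In SAP 4.1.4, state whether the C-GTI and NCOD subperiod analyses take the new term or keep the present model. In SAP 1.4.3, state which NCOD model supplies the interim p-value. If the interim has already been run, which the documents do not say, record that the ranking came from the model without BPDAI and stays as it is. Note the change in SAP 6.1, since protocol 9.3.3.1 names only treatment and the stratification variables.

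The cost is one degree of freedom and these few sentences. No new data are needed.
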